- 2) Subjects who begin with the 13mm device will use the device for a minimum of two weeks during the fitting period. Thereafter, the subject will proceed to the treatment period and will continue using the 13mm device for the entire treatment period.

Following the fitting period, all subjects will then proceed to a 4-week treatment period in which information on fecal incontinence, bowel habits, and global measures will be collected.

After the treatment period, all individuals who withdraw for reasons other than personal preference (i.e., for medical reasons) and a minimum of 50% of all patients shall undergo an evaluation by anoscopy following the treatment period to assess for device related trauma.

The information on fecal incontinence, bowel habits, global measures and adverse events obtained during the bowel diary study (4-week baseline period and the 4-week treatment period) will be used to evaluate the safety and effectiveness of the study device. Adverse events will be collected from enrollment through study exit.

After completing baseline diaries, the following assessments will be performed for informational purposes: 1) All subjects who qualify for treatment with the Minnesota Medical Technologies Anal Insert will undergo a baseline anoscopy, [REDACTED] and [REDACTED] [REDACTED]. 2) Up to [REDACTED] subjects who qualify for treatment with the Minnesota Medical Technologies Anal Insert will undergo [REDACTED] testing with the

Intended Use Statement

study device in place [REDACTED]
The Minnesota Medical Technologies Fecal Incontinence Insert is indicated for the management of accidental bowel leakage (ABL) or fecal incontinence. The rectal insert is designed for self-insertion to seal and help prevent the involuntary leakage of stool from the rectum.

Objectives:

1. **Primary Effectiveness Endpoint:** A relative percentage change in episodes of Accidental Bowel Leakage (ABL) determined by comparing treatment results to pre-treatment results from the baseline period as measured by daily diary recordings.

2. **Exploratory:**
 - Evaluate the effects of the Minnesota Medical Technologies Anal Insert Device on [REDACTED]
[REDACTED].
 - Evaluate if the effects of the Minnesota Medical Technologies Anal Insert Device on symptoms of FI [REDACTED]
[REDACTED] of the device to prevent leakage.
 - Evaluate the [REDACTED] in subjects with FI.
 - Investigate [REDACTED] associated with FI through [REDACTED] at baseline.

Endpoints:

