Overall study duration will be approximately 18 months. Individual subject participation in the study (screening period, baseline period, fitting period, treatment period and post-treatment repeat anoscopy, as applicable,) will be approximately 20 weeks.

[figure not shown]
Study screening procedures will begin after the subject signs the informed consent form. The exception will be allowing subjects who had undergone anorectal manometry within six (6) months prior to signing informed consent. Subjects who underwent a technically adequate standard of care anorectal manometry at Mayo Clinic within six (6) months prior to signing consent will not be required to repeat anorectal manometry, and anorectal manometry results from the standard of care anorectal manometry testing performed within six (6) months prior to consent may

be used for study analysis. There will be a 4-week baseline period followed by an approximately 2 to 4-week fitting period, followed by a four (4) week treatment period. Subjects will also be contacted by telephone to encourage compliance and to assess adverse events. Individual study participation is anticipated to be complete 4 weeks after the last day the device is used. After the treatment period, all individuals who withdraw for reasons other than personal preference (i.e., for medical reasons) and a minimum of 50% of all patients shall undergo an evaluation by anoscopy following the treatment period to assess for device related trauma

While the protocol intends the fitting period to follow directly the baseline period, if needed for scheduling, there can be up to a 7-day interval between the completion of the baseline and initiation of the fitting period. In addition, all study procedures can be performed at \pm 7 days to accommodate scheduling issues.

Subject Duration: The study will consist of a screening visit, a 4-week baseline period, an assessment visit, a 2 to 4-week fitting period, and a 4-week (28-days) treatment period. Allowing for additional days to accommodate scheduling, including repeat anoscopy, if required, the subject participation duration is expected to be approximately 20 weeks.

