1.2 SCHEMA

Study sequence is shown above.

1. Subjects will sign informed consent. At the screening visit, the 10 mm, and, if necessary thereafter, the 13 mm device will be inserted into the rectum to determine if the device stays in situ while subjects are ambulating. Subjects who can retain neither device size will be withdrawn from the study. Subjects who can retain the device will proceed to the baseline period. Subjects will be asked to keep a symptom diary for the 4-week baseline period and complete questionnaires to ascertain if they have FI symptoms of sufficient severity to be considered for treatment. Subjects will be provided with [REDACTED] and a [REDACTED] for use at home during the baseline period.
2. Subjects will return home and record every bowel movement and episode of fecal incontinence in a daily diary for 4 weeks. Subjects will be asked to mail diaries and questionnaires to the study site every week. Subjects will complete the [REDACTED], then [REDACTED] using the [REDACTED]. Subjects will be asked to deliver, or send the [REDACTED] to the study site [REDACTED]. If the diaries and questionnaires are not returned during this baseline period, patients will be contacted.
3. Subjects who have completed the 4-week baseline period and meet criteria for treatment and do not meet any exclusion criteria, will return to the clinic to have assessments (i.e., baseline anoscopy,

[REDACTED], [REDACTED] (if not already performed as within six (6) months of consent), and [REDACTED]).

[REDACTED] sub-study subjects (up to [REDACTED] subjects who agree to [REDACTED] sub-study) will also have [REDACTED] evaluate the effects of the Minnesota Medical Technologies Anal Insert Device on [REDACTED], and to evaluate [REDACTED]. Participants will be enrolled in this sub-study until up to [REDACTED] participants have completed [REDACTED] sub-study. In the event a subject does not wish to participate in [REDACTED] sub-study, but they do wish to participate in the treatment study, they may do so. If they do not wish to participate in the treatment study, their participation in the trial will be terminated and they will exit the study.

[figure not shown]
4. Eligible subjects will proceed to the fitting period which will last up to 4 weeks.

Subjects who did not retain the 10 mm but did retain the 13 mm device at the screening visit will begin the fitting period with the 13 mm device. The sequence of events for the fitting period will be as follows:

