1.3 SCHEDULE OF ACTIVITIES (SOA)

Schedule of Assessments

	Screening visit	Baseline Period (weeks 1-4)	[REDACTED] Sub-Study, as applicable	Fitting Period (up to four weeks after baseline)	Treatment Period* (approximately weeks 9-12)
Day (target) on which this event occurs or begins)	0	Day 1 ¹	Day 28 ²	Approx. day 29 ³	Approx. day 57 ³
Window of days for start of this event	up to six months prior to consent for anorectal manometry	Day 1	Day 28-38 ²	Approximately days 29-45 ³	57-73 ³
Duration	2 hours	28 days	[REDACTED] days	28 days (up to 4 weeks)	28 days (4 weeks)
[REDACTED]		[REDACTED]			
Inclusion/Exclusion criteria review. Includes bowel leakage questionnaire	X	X	X		
Demographics Data form	X				
Informed Consent	X				
Medical history review	X				
Physical examination, including Vital signs ⁴ , height and weight	X				
Concomitant medication review (throughout study from consent to study exit)	X	X	X	X	X
Urine pregnancy test (as applicable)	X				
Teach subject how to complete diaries and	X				

	Screening visit	Baseline Period (weeks 1-4)	[REDACTED] Sub-Study, as applicable	Fitting Period (up to four weeks after baseline)	Treatment Period* (approximately weeks 9-12)
questionnaires					
Teach subject how to use device			X		
Subject's first exposure to study device			X		
Subject daily self-administration of study treatment				X	X
Assess adverse events and medication changes from consent through study exit.	X	X	X	X	X
Guidance is for site to consider calling subjects to remind them to maintain food records for 72 hours before visit to assess anorectal functions ⁵		X			
Anoscopy			X		X* After the treatment period, all individuals who withdraw for reasons other than personal preference (i.e., for medical reasons) and a

	Screening visit	Baseline Period (weeks 1-4)	[REDACTED] Sub-Study, as applicable	Fitting Period (up to four weeks after baseline)	Treatment Period* (approximately weeks 9-12)
					minimum of 50% of all patients shall undergo an evaluation by anoscopy following the treatment period to assess for device related trauma
[REDACTED] data collection form			X [REDACTED] [REDACTED]		
Optional [REDACTED] sub-study with [REDACTED] form			X		
Daily bowel diaries		X		X	X
Global assessment of FI (weekly, during baseline, fitting and treatment periods)		X		X	X

	Screening visit	Baseline Period (weeks 1-4)	[REDACTED] Sub-Study, as applicable	Fitting Period (up to four weeks after baseline)	Treatment Period* (approximately weeks 9-12)

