4 STUDY DESIGN

4.1 OVERALL DESIGN

This is a prospective, open-label, study during which 60 subjects with FI will be treated with the Minnesota Medical Technologies Anal Insert Device. Up to 150 subjects may be enrolled to ensure 60 subjects are eligible to participate in the Treatment Period. This study will consist of a baseline period and a treatment period. A fitting period, prior to the treatment period, will determine which of two devices sizes each study subject will use during the treatment period. Up to [REDACTED] of these 60 subjects will participate in a [REDACTED] sub-study to evaluate the effects of the Minnesota Medical Technologies Anal Insert Device on [REDACTED].

Subjects will sign the informed consent form at the screening visit. After signing the consent form, the subjects are considered enrolled in the study. At this visit, medical history and concomitant medications will be collected, as well as vital signs, and the ability of the subject to retain the device will be evaluated to determine eligibility for the study. Eligible subjects will proceed to baseline period (baseline bowel diary), during which subjects will record all bowel movements in a daily diary and complete questionnaires for 4 weeks. Subjects will be provided with a [REDACTED] and a [REDACTED] for use at home during the baseline period. Subjects will deliver, or send the [REDACTED] to the study site. Subjects who have 4 or more FI episodes during this 4-week baseline period will be eligible to continue to the fitting and treatment periods.

Subjects will return to the Mayo Clinic Rochester study site to have diaries assessed for compliance and eligibility for treatment and, if eligible, will complete quality of life questionnaire. Subjects eligible for treatment will be trained on the insertion and evacuation of the device and will be provided with instructions on how to contact [REDACTED] to have the devices shipped to them.

During this visit to the Mayo Clinic study site, subjects will receive the following assessments: baseline anoscopy (if not already performed within 6 months of informed consent), assessment of [REDACTED], a [REDACTED], and [REDACTED]. In up to [REDACTED] subjects who agree to participate in the [REDACTED] sub-study, [REDACTED] will be assessed [REDACTED].

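### Section 4.1 waives baseline anoscopy after a recent examination, while 1.1 and the Schedule require it of every qualifying subject, so the 5.2 lesion exclusion could rest on an examination about eight months old

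*Combined protocol and SAP*

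**What the plan says.** Section 4.1, describing the return visit after the baseline diaries, lists "baseline anoscopy (if not already performed within 6 months of informed consent" among the assessments. No redaction stands between the procedure and the condition.

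Section 1.1 has no such condition: "All subjects who qualify for treatment with the Minnesota Medical Technologies Anal Insert will undergo a baseline anoscopy". Its lead-in fixes the timing: "After completing baseline diaries, the following assessments will be performed for informational purposes".

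The Anoscopy row of the Schedule (1.3) has a plain mark in the Day 28-38 column and a starred one in the treatment column. The star concerns only the later examination ("X* After the treatment period, all individuals who withdraw for reasons other than personal preference"). The Day 28-38 column carries a sub-study heading, but it also holds eligibility review and device training, so it is the visit for all qualifying subjects.

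Other six-month look-backs:

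- 1.1, Study Duration, names manometry: "The exception will be allowing subjects who had undergone anorectal manometry within six (6) months prior to signing informed consent".
- The Schedule's window row also names manometry: "up to six months prior to consent for anorectal manometry".
- In 1.2, subjects "will return to the clinic to have assessments (i.e., baseline anoscopy". A condition appears later in that list, after a redacted item: "if not already performed as within six (6) months of consent".
- 7.1 has one under a redacted heading.

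Section 5.2 excludes subjects with a fissure, thrombosed external hemorrhoids, or internal hemorrhoids of Grade III or IV on anoscopy. Section 4.1 also plans post-treatment anoscopy, in at least half of the patients and in all who withdraw for medical reasons, to look for trauma from the device.

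**The concern.** A site with a recent anoscopy on file has two incompatible instructions. Skipping the examination departs from 1.1 and the Schedule; repeating it ignores 4.1.

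The conflict is more than clerical. Although 1.1 calls these assessments informational, 5.2 uses the anoscopy to decide who may go on. If an old examination is accepted, a lesion that arose since then and causes few or no symptoms could pass into home use unseen. The same kind of lesion found after treatment would be hard to attribute: 8.2 gives anal fissure as its example of the side effect that post-treatment anoscopy should detect, and fissure is one of the lesions that 5.2 screens out.

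**Working it through.** The plan gives no figure for the age of the examination, so the check sets the texts side by side and then works out the dates.

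**Texts**

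| Place | Who has baseline anoscopy | Six-month look-back |
|---|---|---|
| 1.1 | all who qualify, after the diaries | manometry only, by name |
| 1.2 | listed at the return visit | present, scope redacted |
| 1.3 Schedule | marked at Day 28-38 | manometry only, by name |
| 4.1 | listed at the return visit | attached to anoscopy |

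The firm conflict is 4.1 against 1.1, with the Schedule on the side of 1.1.

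**Inputs for the dates**

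- Consent is signed at the screening visit (4.1).
- Screening is at most 21 days before Day 1 (Schedule, footnote 1).
- The assessment visit falls on Days 28-38 and generally lasts 1-2 days (footnote 2).
- The fitting period starts on about Days 29-45 (Schedule).
- The next period starts within 7 days after the assessment is complete (footnote 3). The footnote speaks of treatment, but its marker is also on the fitting column, and 38 + 7 = 45 matches the end of the fitting window.
- Six months is taken as 183 days (an assumption; 181-184 moves each result under 4.1 by -2 to +1 day).

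**Age of the examination if 4.1 is followed, at most**

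- At the latest visit, Day 38, which is 37 days after Day 1: 183 + 21 + 37 = 241 days (239-242).
- At the latest start of fitting, Day 45, which is 44 days after Day 1: 183 + 21 + 44 = 248 days (246-249).
- On the target schedule, with screening on Day 0 and the visit on Day 28: 183 + 28 = 211 days.
- On the last treatment day, after 28 days of fitting and 28 of treatment: 248 + 28 + 27 = 303 days.

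**Age if 1.1 and the Schedule are followed**

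- At the visit: 0 days.
- At the start of fitting: 7 days plus a visit of 1-2 days, so roughly 7-9 days.
- On the last treatment day: 7 + 55 = 62 to 9 + 55 = 64 days.

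The general 7-day allowance for procedures is left out throughout. The lower bound under 4.1 is near 0, since an examination close to consent also satisfies the waiver.

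**Why one missed lesion matters.** Section 8.2 states 80% and 96% power with 31 patients for event rates of 5% and 10%. These match the chance of seeing at least one event: 1 - 0.95^31 = 79.6% and 1 - 0.90^31 = 96.2%. On that criterion, a single pre-existing fissure missed at entry could supply the event. The waiver does not change the 31; it affects how a finding is read.

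**The case against.** The best defence is that 4.1 merely says how the 1.1 requirement may be met, with a recent examination standing in as the baseline one, and that a synopsis or grid may omit such detail. That would reconcile who is examined. It does not reconcile when, because 1.1 places the assessment after the baseline diaries.

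Redaction also limits what can be said. A reader might infer that 1.2 lists anoscopy free of any waiver. The documents do not support this: a six-month condition stands later in that list, and its scope cannot be seen. The same goes for the look-back in 7.1. Manometry is the likelier subject of both, but this cannot be shown. Nor can it be settled whether the parenthesis in 4.1 is deliberate or a misplaced manometry waiver.

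Three stronger readings should be resisted:

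- A reader might infer that a waived subject has no examination to which 5.2 can be applied. The 5.2 wording can mean an examination made after baseline, but it can equally mean findings from the baseline anoscopy. On the second reading the exclusion applies to the older examination, and only its age is at issue.
- A reader might take the Day 28-38 anoscopy for a record of the anorectum before any device use. It precedes home use only, because 1.1, 1.2 and 6.1.2 have the device inserted at screening. (The Schedule's first-exposure row says otherwise.) Its role as reference for the post-treatment anoscopy is also an inference; no section prescribes that comparison.
- A reader might infer bias in the primary endpoint. That endpoint comes from diaries. The only route is indirect: under 6.7 a significant abnormality leads to study exit, and data from patients withdrawn for an adverse event leave the effectiveness summary.

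The safeguards are real: a rectal examination after consent (7.2), exclusion for pain or bleeding in the past month (5.2), repeated eligibility review (1.3), withdrawal of subjects who come to meet an exclusion (5.4), and anoscopy triggered by symptoms (7.1, 7.3.8). None is a routine look for silent lesions just before home use.

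**Conclusion.** The conflict stands on unredacted text and should be corrected. If 4.1 governs, the examination behind the 5.2 exclusion could be up to about 241 days old at the visit and about 248 days old at the start of home use, against roughly 7-9 days at the start of fitting under 1.1 and the Schedule.

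The larger figures need an examination a full six months before consent, the whole 21-day screening gap and the latest windows together; they are limits, not typical values. What remains after the safeguards is a small risk, confined to silent or mildly symptomatic lesions in subjects with a prior anoscopy. The documents do not say how many such subjects there would be, and there may be none. The point concerns eligibility and the reading of safety findings, and does not directly affect the primary endpoint. Confidence is medium, because the intent behind the parenthesis is unknown.

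**What to change.** In 4.1, delete the parenthesis after baseline anoscopy, or attach it to anorectal manometry if that was the intention. Every qualifying subject then has anoscopy at the post-baseline visit before home use. State in 5.2 that the lesion exclusion is applied to that examination.

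The edit is one phrase in 4.1 and a clarification in 5.2. The cost is a few repeat anoscopies, with their discomfort, in recently examined subjects. 1.1 and the Schedule already call for these, at a visit that the subjects attend anyway.

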4.2 SCIENTIFIC RATIONALE FOR STUDY DESIGN

Because existing approaches to manage FI are of limited efficacy,⁴ there is an unmet need for additional approaches to manage this symptom, which can have a potentially devastating impact on QOL. A systematic review observed that while anal plugs might be helpful in some patients, they are poorly tolerated, with a dropout rate ranging from 12.5% to 68% across the four studies³². Another device, the Renew anal insert device (Renew Medical Inc., Foster City, CA), is approved for treating FI in the United States. In the intent-to-treat analysis, 62% of patients achieved $\geq 50\%$ reduction in the frequency of FI with that device.⁷ The Minnesota Medical Technologies Anal Insert Device is designed to engage with and conform to the anorectal junction and the anal canal to provide an anatomical fit in order to protect against bypass leakage. The device is very soft and pliable which is expected to provide superior performance relative to devices which are currently on the market, with relatively few adverse events and good patient acceptance.

4.3 JUSTIFICATION FOR TREATMENT

The treatment of anal leakage and bowel incontinence includes a range of treatments from lifestyle changes to surgical options. This study is designed to evaluate a low-risk, minimally invasive self-insertion anal device to help block anal leakage and bowel incontinence by assisting the body in forming a seal to reduce or block leakage.

The Minnesota Medical Technologies Anal Insert Device size was selected for design based on studies that characterized the anal canal in subjects with anorectal disorders. Among a cohort 119 patients with anorectal disorders, 49 patients (41%) had a patulous anal canal, which was more common in patients with FI (58%) than constipation (25%).⁵ A patulous canal is associated with, and likely consequent to injury to the anal sphincters and pelvic floor muscles. It predisposes to fecal leakage. In that study, the anal canal diameter was \leq 10 mm in 39 of 49 patients with a patulous canal; in the remainder, the diameter was between 10 and 20 mm. Hence, the Minnesota Medical Technologies Anal Insert Device will be available in two sizes (i.e., 10mm and 13mm).

4.4 END OF STUDY DEFINITION

Subject participation is voluntary, and subjects may leave the study at any time. Subjects will be instructed to contact their doctor if they choose to leave the study, to make arrangements for standard of care treatment of their fecal incontinence moving forward and to assess if the subjects experienced any adverse events. The study sponsor or the U.S. Food and Drug Administration may decide to stop the study at any time. The study investigators may decide that participation in the study is not in the subject's best interest for health reasons.

A subject is considered to have withdrawn or been withdrawn from the study, or if the subject has completed all phases of the study including the last visit or the last scheduled procedure shown in the Schedule of Activities (SoA), Section 1.3. The end of the study is defined as completion of the last subject's last visit or procedure shown in the SoA in the trial globally.

